6.2 Secondary Endpoints- Statistical Methods

Analysis Plan. To address secondary objectives, we will follow the identical procedure outlined above, but will swap in the relevant outcome as the dependent variable (i.e., cortisol, salivary alpha amylase, PEP, RSA, psychological responses). We will first examine if there was a change in the outcome simply as an effect of taking the propranolol (before stress induction). As such, we will conduct a multilevel model (MLM) examining levels of the outcome, with time (BL vs. pre-TSST) as a within-subjects factor and condition (propranolol vs. placebo) as a between-subjects factor. If the result of this test shows a significant interaction, then we will only include the pre-TSST time point in subsequent models. If non-significant, we will use both baseline time points in subsequent analyses. Next, we will conduct an MLM examining levels

of each relevant outcome, with time (BL and/or pre-TSST, post-TSST time-points) as a within-subjects factor and condition (propranolol vs. placebo) as a between-subjects factor.

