4.1 Intervention/Treatment procedures (by visits)

Session II (the intervention/treatment visit) will last approximately 5 hours and will take place in the emotion induction laboratory in Howell Hall at UNC-CH. When the participant arrives for the session, they will meet the lab manager and the nurse supplied by CTRC. The lab manager will give the participant a chance to review the consent form they signed during Session I, and will then remind the participant of the protocol and tasks in Session II. Once the participant understands the protocol and is comfortable with proceeding, the nurse will insert a catheter into the participant's non-dominant forearm, which will be used to draw all the blood samples. We use the catheter method so that participants do not have to be stuck with needles multiple times throughout the experiment. Once the catheter is placed, the participant will be given at least 45 minutes to acclimate to the catheter, during which time they will be prepared for psychophysiological data collection. We are collecting Heart Rate, Respiratory Sinus Arrhythmia, Cardiac Impedance, and Blood Pressure measures from participants throughout the session and, which will allow us to get a good index of participants' autonomic nervous system responses to the stress task, and will provide a biological "manipulation check" to ensure that the propranolol has had the intended effect (it should lower heart rate and blood pressure). Again, as with

Session 1, female research assistants will be assigned to female participants, while both male and female research assistants will be assigned to male participants, in an effort to reduce participant discomfort with the procedure of attaching the sensors. Once sensors have been attached, we will collect 5 minutes of baseline data while the participant just rests and relaxes.

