Upon completion of the baseline psychophysiological measures, participants will complete trait questionnaire measures while they continue to acclimate to the catheter and the laboratory environment. Once 45 minutes has passed (around 1:15 PM), the nurse will draw the first (baseline) blood sample, and participants will be asked to provide the first (baseline) saliva sample. Next, the oral tablet of propranolol or placebo will be administered to the participant by the nurse. Participants will continue completing trait questionnaires and once finished, they will be given neutral reading material (magazines) to read while drug activation takes place. One hour after administration of the medication (or placebo), the nurse will draw a second blood sample, and participants will be asked to provide a second saliva sample. We will also collect another 5 minutes of psychophysiological data.

Next, the Trier Social Stress Task (TSST; Kirschbaum, Pirke, & Hellhammer) procedures will be explained to participants. The TSST is a commonly-used acute stress test to measure psychological and biological responses to stress in the laboratory. In this task, participants will be asked to prepare for and give a 10-minute speech and complete a difficult mental arithmetic task as they are evaluated by trained interviewers. The nature of the task is stressful and participants may experience varying levels of stress, anxiety, and possibly embarrassment. The consent form at the beginning of the study describes that they will take part in a “role play” during a cognitive performance task (see Consent Form). We describe the task in this vague way in the initial consent because we want to ensure that the baseline physiology data is clean and not impacted by participants' anticipatory stress about the upcoming task. Additionally, prior to the participant's participation in the TSST, participants will be informed in greater detail about the procedure for TSST, and they will be asked if they would like to continue. If they do continue, but wish to stop at any time, they will be reminded that they can.

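### Section 6.2 needs baseline and pre-TSST values of negative affect, but Sections 4.1 and 5 describe no affect rating before the stressor

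*Combined protocol and SAP*

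**What the plan says.** Section 6.2 uses the primary procedure for every secondary outcome, changing only the dependent variable: "but will swap in the relevant outcome as the dependent variable (i.e., cortisol, salivary alpha amylase, PEP, RSA, psychological responses". Section 2.2 identifies the psychological response as negative affect (Secondary Objective 5), and the synopsis also names negative affect among the outcomes to be modelled.

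The procedure has two steps. Step 1 tests baseline (BL) against pre-TSST by condition, to see whether the drug alone moves the outcome. If the interaction is significant, only the pre-TSST point goes forward. Otherwise the rule is: "If non-significant, we will use both baseline time points in subsequent analyses". Step 2 models BL and/or pre-TSST together with the post-TSST points, by condition.

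Section 4.1 (Intervention/Treatment procedures) sets out Session II in order:

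- **Before dosing, psychophysiology:** "Once sensors have been attached, we will collect 5 minutes of baseline data while the participant just rests and relaxes".
- **Before dosing, questionnaires:** "participants will complete trait questionnaire measures while they continue to acclimate to the catheter and the laboratory environment".
- **Baseline draw:** "the nurse will draw the first (baseline) blood sample, and participants will be asked to provide the first (baseline) saliva sample".
- **Hour after dosing:** "Participants will continue completing trait questionnaires and once finished, they will be given neutral reading material (magazines) to read while drug activation takes place".
- **Pre-TSST stop:** "the nurse will draw a second blood sample, and participants will be asked to provide a second saliva sample". The next sentence adds: "We will also collect another 5 minutes of psychophysiological data".
- **After the TSST:** a second round of questionnaires, the first one described as measuring affective responses.

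Section 5 describes the PANAS-circumplex as covering emotions felt during the TSST and feelings at the time of rating. It gives no occasion before the TSST.

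**The concern.** Both steps of Section 6.2 need affect measured before the stressor, and the described schedule supplies none. Saliva and psychophysiology are each collected at BL and at pre-TSST, so the gap is specific to affect.

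What is at stake is the meaning of Objective 5, which asks about the affective response to a stressor. Propranolol might shift mood directly during the hour before the TSST, or it might change how people react to the TSST. Step 1 exists to tell these apart. Ratings taken only after the TSST cannot do so, and a pre-stress rating that was not taken cannot be recovered later.

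**Working it through.** The documents state no figure on this point, so there is none to reproduce. The check sets the time points that the models need against the ratings that are described.

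**1. Needed against described**

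| Occasion | Needed for affect (6.2) | Described (4.1, 5) |
|---|---|---|
| BL, before dosing | Step 1; step 2 if step 1 is non-significant | Psychophysiology, trait questionnaires, blood, saliva; no affect rating |
| Pre-TSST, 1 h after dosing | Steps 1 and 2 | Blood, saliva, psychophysiology; no affect rating |
| Post-TSST | Step 2 | One affect administration with two framings (recalled from the TSST; current) |

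**2. What can be estimated**

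- Step 1 has 4 fixed-effect columns: intercept, condition, time, condition × time. With ratings at both points the rank is 4 of 4. As described there are no rows of affect data.
- Step 2 with BL, pre-TSST and post-TSST has 1 + 1 + 2 + 2 = 6 columns. With all three occasions the rank is 6 of 6. With post-TSST only there are two distinct rows, one per arm, so the rank is 2 of 6. The post-TSST arm difference is estimable; condition × (pre-to-post change) is not.
- With one current rating per person, the random intercept also cannot be separated from the residual. Using the two post-TSST framings as the time factor would compare recalled with current affect, not post-stress with pre-stress affect.

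**3. Sensitivity of the two comparisons**

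Inputs: 45 per arm (Section 6.4); alpha 0.05 (Section 6), read as two-sided; 80% power (assumed); equal SDs and pre/post correlation r (assumed, since the documents give none).

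- Post-only: (1.960 + 0.842) × √(2/45) = 0.59 SD. The t-based value is 0.597.
- Pre-TSST-to-post contrast: 0.597 × √(2(1 − r)) = 0.755, 0.597 and 0.463 SD at r = 0.2, 0.5 and 0.7.

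The contrast is less sensitive than post-only when r is below 0.5 and more sensitive above it.

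**4. Illustration only: what a direct mood effect would do**

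Assume the drug shifts mood by d SD equally at pre-TSST and post-TSST and leaves the stress response unchanged. Equal shift is an assumption. Pre-TSST is 60 min after dosing, and the TSST ends at least 60 + 5 + 2 + 10 + 5 = 82 min after dosing; both fall in the 1-2 h peak window of Section 1.3.

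- Post-only comparison: noncentrality d × √(45/2) = 0.95, 1.42 and 2.37 for d = 0.2, 0.3 and 0.5. It is significant in about 16%, 29% and 65% of trials.
- Pre-TSST-to-post contrast: about 5% throughout.
- The existing two-step rule, simulated with r = 0.2, 0.5 and 0.7: 5-8%, 8-11% and 10-13%.

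These show that the comparisons answer different questions. They are not error rates: in this scenario affect really does differ between the arms after the TSST.

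**The case against.** The best case on the other side is that the documents are silent about timing and never say that pre-stress affect is not measured. A second round of questionnaires implies a first. Section 3.1 promises a series of questionnaires over the five hours. The PANAS includes current feelings, the State-Trait Anxiety Inventory is untimed, and Section 10 refers to flow sheets that set questionnaire times. Section 6.2 itself presupposes the values.

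Part of this stands. A reader might infer that no pre-stress affect is collected; the documents support only that none is described. But nothing cited places a rating at BL or pre-TSST. The only earlier round described consists of trait measures. The anxiety inventory is listed among questionnaires for exploratory moderator analyses, is not named as the negative-affect endpoint, and given once would not supply both values.

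It is also fair to say that the randomised comparison of affect during or after the TSST remains valid. A reader might take the 16%, 29% and 65% as false-positive rates, or conclude that Objective 5 cannot be answered at all. Neither follows: the post-only comparison estimates the drug's total effect and partly answers the objective.

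Finally, one might want to drop the step 1 rule for affect and test a fixed pre-TSST-to-post contrast whatever step 1 shows. That is a separate question about the two-step rule, and it is optional here. Nor should the current-feeling score displace the recalled one. It is taken after the TSST with no stated delay and may partly reflect recovery.

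**Conclusion.** Taken as written, Section 6.2 cannot be carried out for negative affect: step 1 has no data, step 2 has no pre-stress level, and only a post-TSST arm difference is estimable. This conclusion rests on the text alone and needs no assumed effect size. It is conditional on the flow sheets, which may already schedule the ratings.

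The consequence is limited to one of five secondary objectives. What is lost there is the pre-to-post response and the separation of a direct mood effect from a changed stress response. The primary IL-6 analysis is unaffected. The sensitivity and mood-shift figures depend on assumed correlations and shifts and do not bear on whether the gap exists. It should be corrected, because an analysis stated for a named objective has no described data and the remedy is cheap.

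**What to change.** - **Preferred.** In Section 4.1, give the PANAS current-feeling items at the baseline draw (before dosing) and at the pre-TSST draw, both before the TSST is explained, and keep the post-TSST ratings. The Section 6.2 procedure can then be run for affect on the current-feeling score. Report the recalled during-TSST score alongside it as a between-group comparison, noting that it does not separate out a direct mood effect.
- **If the flow sheets already schedule these ratings.** State the instrument, score and times in Sections 4.1 and 5.
- **If the schedule is not changed.** For negative affect, replace the shared procedure in Section 6.2 with a post-TSST between-group comparison, and limit the conclusion to affect during and after the stressor under drug.

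The cost is a few minutes of questionnaire at two existing stops, plus wording in Sections 4.1, 5 and 6.2. No extra visit, sample or participant is needed. The statistical price is that a pre-to-post contrast is less sensitive than a post-only comparison if the pre/post correlation is below 0.5.

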6.4 Sample Size and Power

We are planning to enroll 45 participants per condition in our study, for a total of 90 participants. The sample size was selected based on a thorough literature review of prior studies that have examined the effects of propranolol on psychological tasks in healthy participants (similar to those in the present study) revealed the average sample size of each condition to be 21 participants (22 in the propranolol condition, 21 in the placebo condition). Thus, by randomizing 45 participants to each condition, we are sufficiently powered to achieve our aims. We have included more participants than prior work in this area because we are interested in examining *moderators* of our main effects of interest, and such analyses require greater sample size to be sufficiently-powered. We also considered availability of possible eligible participants when making this decision; we do not anticipate significant difficulty in finding participants who meet our inclusion/exclusion criteria, given that they are relatively open and should be relatively prevalent in our target recruitment population (i.e., primarily healthy, undergraduate students). Finally, we also considered practical constraints in terms of funds and time available to complete the study. As the project will be funded off of [name] laboratory start-up funds, we do not currently have grant funds to enroll additional participants. We are also hoping to complete the project within one year so that we can use the data generated by the project as preliminary data for a grant to be submitted to NIH to run a similar study including a neuroimaging (fMRI) component.

7. STUDY INTERVENTION (drug, device or other intervention details)

Description. Propranolol blocks the effect of epinephrine and norepinephrine by competitively binding to on both β_1 - and β_2 -adrenergic receptors in both the peripheral and central nervous system. It was originally used to treat hypertension, approved by the FDA in 1965. Since then it has been FDA approved for a variety of other indications, including migraine prevention, and essential tremor. It is even approved for certain pediatric conditions. Propranolol is one of the historically most commonly-used prescription medications, and it is generally viewed as a safe, nontoxic medication in the daily dosage range of up to 640 mg, divided into 2-4 doses per day.

Receipt/Storage. The project manager will pick up the medication at IDS the day prior to the participants second session. All medication tablets will be stored in a room temperature locked cabinet in the [name] Lab in Howell Hall at UNC. Only the project coordinator and the PI will have a key for this cabinet.

Packaging/Labeling. Medication will be packaged and labeled in accordance with IDS protocol.

Dosing. Each participant will receive 40mg of propranolol, or a tablet of equivalent size of a placebo.

Treatment compliance and Adherence. This is a one-time dosage, so not applicable.

Drug Return/Destruction. If a participant does not show up for their appointment, we will return the drug to IDS and they will destroy it in accordance with their protocol.

8. STUDY INTERVENTION ADMINISTRATION (if applicable)

This is a double blind, randomized clinical trial. IDS will randomly assign patients to the experimental group (propranolol) or the placebo group. Research staff who have direct contact with the participant will be blind to the condition of the participant. The psychiatrist who is monitoring safety and possible adverse events while the participants are on propranolol or placebo will be unblinded during the study and therefore able to identify which pill was taken if there are any significant adverse effects felt by the participant after taking the pill. The psychiatrist will not have direct contact with participants during the experimental visits unless the participant is experiencing adverse side-effects. Thus, no study team member who interacts with participants on the propranolol/placebo Session II visit will know whether a participant is on placebo or propranolol. After data collection for the study is completed, the pharmacist who made order assignments will reveal which group participants were in (propranolol vs. placebo) so appropriate analyses can be conducted.

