1 BACKGROUND AND RATIONALE

1.1 Introduction

Psychological stress is implicated in the onset and progression of many common and costly chronic diseases, including cardiovascular disease, chronic pain conditions, and major depressive disorder (Cohen et al., 2007; Kendler et al., 1999; Steptoe and Kivimäki, 2012). An emerging body of evidence suggests that inflammation, indexed via levels of pro-inflammatory cytokines and reactive proteins, may be a key biological mechanism by which stress affects health (Baker et al., 2012; Miller et al., 2009; Slavich et al., 2010). Indeed, psychological stressors can induce increases in inflammation (Slavich and Irwin, 2014; Kiecolt-Glaser et al., 2003; Rohleder, 2014; Steptoe et al., 2007), and greater levels of inflammation may contribute to the development of disease (Capuron and Miller, 2004; Choy and Panayi, 2001; DellaGiola and Hannestad, 2010; Raison and Miller, 2013; The Emerging Risk Factors Collaboration, 2010). Despite this growing literature linking stress, inflammation, and poor health, little is known about the precise physiological mechanisms linking psychological stress and increases in inflammation.

One hypothesized mechanism that may translate psychological stress into increases in levels of inflammation is activation of the sympathetic nervous system (SNS). The SNS is part of the autonomic nervous system and is primarily indexed by release of the catecholamines epinephrine (adrenaline) and norepinephrine (noradrenaline). Prior research in non-human animal models has shown that stress-induced SNS activation leads to increases in levels of pro-inflammatory cytokines in inflammation (Bierhaus et al., 2003; DeRijk et al., 1994; Kop et al., 2008; van Gool et al., 1990), while pharmacologically blocking sympathetic activation attenuates the inflammatory response to stress (Bierhaus et al., 2003). However, no known human studies to date have examined the relationship between psychological stress, SNS activation, and inflammation. The present study is designed to address this major gap in our knowledge of the physiological mechanisms that may link stress and disease.

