To circumvent these issues with assessment of SNS activity, the present study will employ a psychopharmacological approach to experimentally block SNS activity using the drug propranolol. Propranolol is a beta-blocker medication that is very commonly prescribed by physicians in the United States for the treatment of hypertension, given that it blocks adrenergic receptors that lead to relaxation of the cardiac muscle and smooth muscle tissue. Interestingly, propranolol is also sometimes prescribed to individuals who have performance anxiety (i.e., public speaking anxiety), as reducing SNS activity (i.e., eliminating the increased heart rate, blood pressure, sweaty palms, etc., that typically accompany anxiety-provoking situations) has been anecdotally observed to decrease perceptions of stress during these situations. Psychological scientists have recently become more interested in the role SNS activity may play in the formation and reconsolidation of fear memories, and a number of studies have now used propranolol to investigate if blocking SNS activity may help treat individuals with Post-Traumatic Stress Disorder (PTSD; Pitman et al., 2002; Vaiva et al., 2003). However, only one known study to date has investigated if propranolol reduces stress-induced immune system activation (Benschop et al., 1994), and this (now dated) study did not specifically explore if propranolol reduces inflammatory responses to stress. Furthermore, no known studies have examined if blocking SNS activity with propranolol changes individuals' appraisals of the stressful situation, or their affective responses to stress. Results from this study will complement and extend the existing work on how SNS activity affects fear memories and stress by focusing on how propranolol affects inflammatory and psychological responses to a stressor.

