Saliva Samples. We will take 4 saliva samples during the study via the passive drool method. Passive drool is a saliva collection method for collecting whole saliva. Passive drool is considered by many researchers to be the gold standard when collecting saliva samples for biological testing, because it provides the purest sample possible and allows researchers to "biobank" samples for testing. Participants allow saliva to pool in mouth, then, with head tilted forward, gently force saliva through a small straw and into the vial. Participants will be aided by trained research assistants wearing rubber gloves. About 2ml of saliva will be collected at each sampling time. Saliva samples will be assayed for levels of the stress hormone, cortisol, as well as another HPA axis byproducts including ACTH and testosterone.

Blood Samples. We will draw 10 mL of blood into vacutainer EDTA tubes at each time point, which will be stored on ice for the duration of the study, and then centrifuged to isolate plasma and stored in 1 mL aliquots in cryovials in a -80 degree freezer until the study is complete. Samples will then be assayed for levels of pro-inflammatory cytokines (i.e., interleukin-6, tumor necrosis factor alpha, interleukin-1) using multiplex bead-based assays.

Psychophysiology. We will collect electrocardiogram and impedance cardiography data from participants to examine how propranolol and exposure to the TSST influence autonomic physiology.

Questionnaires (for exploratory moderator analyese):

Demographics.

We ask participants' age, gender, race/ethnicity, weight/height (to calculate BMI), perceived SES, and also about participants' comfort with giving speeches / being the center of attention.

Health Behavioral Questionnaire ([name], 2016). This asks a series of questions to make sure that participants followed instructions prior to the session and are still eligible to participate. It includes items "Which medications have you taken in the last 48 hours?"

UCLA Loneliness Scale: (Russell, D., Peplau, L.A., and Ferguson, M.L 1978) This is a commonly used, 10 item, measure of loneliness.

The PHQ-9: (Spitzer, 1999) This a multipurpose, validated instrument for screening, diagnosing, monitoring and measuring the severity of depression.

Perceived Stress Scale: (Cohen, 1994) This is a widely used psychological instrument for measuring the perception of stress; i.e the degree to which situations in one's life are appraised as stressful.

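### Does the unsupported claim of sufficient power at 45 per condition call for a change to Section 6.4?

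*Combined protocol and SAP*

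**What the plan says.** Section 6.4 plans 45 participants per condition, 90 in total. The synopsis and Section 3.3 give 95; the synopsis explains the five extra as cover for data loss. The stated basis is a literature review of propranolol studies of psychological tasks in healthy people, which "revealed the average sample size of each condition to be 21 participants (22 in the propranolol condition, 21 in the placebo condition"). From this the section infers that "by randomizing 45 participants to each condition, we are sufficiently powered to achieve our aims".

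The section then explains why the number exceeds earlier work. "We have included more participants than prior work in this area because we are interested in examining" moderators, it says, and "such analyses require greater sample size to be sufficiently-powered". It adds availability of participants and then resources: "Finally, we also considered practical constraints in terms of funds and time available to complete the study".

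Four other places bear on this:

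- Section 1.1 says that "no known human studies to date have examined the relationship between psychological stress, SNS activation, and inflammation", and that the one earlier propranolol study of stress and immune activation ("study did not specifically explore if propranolol reduces inflammatory responses to stress") does not fill the gap.
- Section 5 introduces the trait measures as "Questionnaires (for exploratory moderator analyese").
- Section 6 uses 95% confidence intervals and a .05 threshold, and leaves results above it uninterpreted.
- Section 6.1 specifies a random-intercept model for IL-6 with condition and four or five time points. Neither 6.1 nor 6.2 specifies a moderator model.

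**The concern.** The size of earlier studies is not evidence of power. It shows what others could afford or chose to run, not what effect they could detect, and those studies measured psychological tasks rather than IL-6. A statement of adequate power normally rests on an effect size, a variance and a target power, and none of these appears anywhere in the document.

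The moderator argument looks weak for a similar reason. Moderator tests do need larger samples, as the section says, but roughly doubling the arm size is not shown to be enough.

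What would be at stake is how results are read. Told that the study was adequately powered, a reader might take a null IL-6 result as evidence against the sympathetic mechanism, or take a significant moderator as one the study was sized to test.

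**Working it through.** **The plan's own figure.** There is nothing to reproduce. Section 6.4 states a number of participants but no power, effect size, SD or within-person correlation. The only arithmetic available is the ratio to earlier work: 45/21 = 2.14, or 45/21.5 = 2.09 using the mean of 22 and 21. The section's figure of 21 is that 21.5 rounded down, which is of no consequence.

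**What 45 per condition can detect on IL-6.** Inputs from the plan: n = 45 per condition; level .05, taken as two-sided; three post-stress draws; two pre-stress draws, or one if the preliminary test in Section 6.1 is significant. Assumptions: random-intercept model, the same condition difference δ at 30, 60 and 90 minutes, complete data. The unit of δ is the residual (within-person) SD of the analysed IL-6 variable.

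Noncentrality = (n/2) × S × δ², with S = pre × post / (pre + post).

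- Five time points: S = 2 × 3 / 5 = 1.2, so noncentrality = 22.5 × 1.2 × δ² = 27δ².
- Four time points: S = 1 × 3 / 4 = 0.75, so noncentrality = 22.5 × 0.75 × δ² = 16.875δ².

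Section 6.1 names the factors but not the test. Two readings are reasonable: an omnibus condition-by-time F test (4 or 3 df), or a one-df pre-to-post contrast, which suits the directional hypothesis and the confidence-interval rule.

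| Time points | Test | df | δ at 80% power | Power at δ = 0.5 | Power at δ = 0.3 |
|---|---|---|---|---|---|
| Five | Omnibus | 4, 352 | 0.67 | 52% | 20% |
| Five | One-df contrast | 1, 352 | 0.54 | 74% | 34% |
| Four | Omnibus | 3, 264 | 0.81 | 37% | 15% |
| Four | One-df contrast | 1, 264 | 0.68 | 54% | 23% |

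As a check, 27 × 0.669² = 12.1 and 27 × 0.541² = 7.9, the noncentralities needed for 80% power with 4 and 1 numerator df. Section 6.1 expects no rise on propranolol, so under full blockade δ is the placebo group's own rise. The documents do not give that rise in any unit, so the table cannot show whether 45 is too few.

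**Moderators.** Section 6.4 gives no power for the earlier studies. Suppose 22 and 21 gave 80% power for a condition effect on one per-person contrast. That requires d = 0.875 contrast SDs (SE = √(1/22 + 1/21) = 0.305, 41 df). For a moderator splitting each arm evenly, the SE of the difference between the two condition effects is √(8/45) = 0.422, with 2 × 45 − 4 = 86 df.

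- Moderator difference equal to the effect: 0.875/0.422 = 2.08, power 54%. About 83 per condition would be needed for 80%.
- Half the effect: power 18%.
- Twice the effect (absent in one half, doubled in the other): power 98%.
- 80% power is reached at a difference of 1.195, and 1.195/0.875 is about 1.36 times the effect.

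If 22/21 gave 50% or 90% power instead, the 54% becomes 30% or 66%. These figures rest on assumptions the plan does not make, so they show that moderator power is undemonstrated, not that the plan contradicts itself.

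**The case for a change.** The strongest case for a change is that the inference is plainly invalid and cheap to remove. Two sentences in Section 6.4 could be replaced by a statement that the number reflects earlier study sizes, availability, funds and time, with no power claimed for moderators. The practical reasons justify the number; they do not justify calling it powered. The .05 rule in Section 6 has no exemption for exploratory tests, and Section 6.4 itself ties the larger sample to moderators, so a significant one could be over-read.

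The criticism of the sentence stands. What does not stand is the stronger argument built on it. A minimum placebo rise of 0.67 residual SD holds only for an omnibus test that Section 6.1 does not name; a one-df contrast needs 0.54. Writing either figure into the protocol alone would imply a choice of test the plan has not made. Nor can the design be said to serve only very large moderators when, on the assumed 80% benchmark, about 1.36 times the condition effect suffices. Earlier psychological-task studies also have some relevance to the psychological aims, though none to IL-6. Taking moderators out of the p-value rule would be a preference, not a correction of a power statement.

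**Conclusion.** The claim of sufficient power is unsupported for IL-6 and for moderators, but it is not shown to be false. At 45 per condition, 80% power is reached at 0.54 to 0.67 residual SD with five time points and 0.68 to 0.81 with four, given a random intercept, a constant post-stress difference and complete data. Whether that is adequate depends on a within-person SD and a stress response that the documents do not supply.

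No change follows. No stated power figure is missed, and choosing the number partly on funds, time and availability is a fair and openly declared trade-off for a first human study of this question. The two feared misreadings are already limited by the rule against interpreting non-significant tests and by the exploratory label on the moderator measures. An analyst can report estimates with confidence intervals and treat the power sentence as a judgement. Editing it would be a minor wording improvement that leaves the sample size, the primary analysis and every result as they are.
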